9.3. Method of Assignment to Treatment

All enrolled patients will receive ALXN1210.

9.4. Rationale for Selection of Doses in the Study

The weight-based dosages of ALXN1210 in this study (Table 6) are premised on PK/PD data from early development studies in healthy adult volunteers as well as the available data from patients with PNH in an ongoing Phase 1b dose-finding study (ALXN1210-PNH-103) and an ongoing Phase 2 proof-of-concept study (ALXN1210-PNH-201). The selection of the ALXN1210 dose regimen is based on targeting immediate, complete, and sustained inhibition of terminal complement in pediatric patients with PNH throughout the dosing interval. Body weight-based dosing in pediatric patients is proposed to limit body weight-based variability in ALXN1210 drug exposure. ALXN1210 pediatric dosing is predicted to not exceed maximum ALXN1210 exposures achieved in PNH patients in Phase 2.

9.5. Special Treatment Considerations

Infusion of other monoclonal antibodies has been associated with infusion reactions, with onset typically during or shortly after completion of the infusion. Please refer to Appendix B for guidance on identifying and managing potential drug infusion reactions.

9.6. Blinding

This is an open-label study, so blinding is not applicable.

9.7. Prior and Concomitant Medications and Nonpharmacologic Procedures

Prior medications (including vitamins and herbal preparations)—including those discussed in the exclusion criteria (Section 8.2) and procedures (any therapeutic intervention, such as surgery/biopsy or physical therapy) the patient takes or undergoes within 28 days prior to the start of Screening until the first dose of study drug—will be recorded on the patient's eCRF. In addition, history of meningococcal vaccination must be collected for the 3 years prior to first dose of study drug and vaccination history for Hib and *S pneumoniae* must be collected from birth.

If patients had been treated with eculizumab, a documented regimen history will be collected. Transfusions of pRBCs received within 1 year prior to first study drug administration will be recorded on the patient's eCRF.

All medication used and procedures undertaken during the study will be recorded in the patient's source document/medical chart and eCRF. This record will include all prescription drugs, herbal products, vitamins, minerals, over-the-counter medications, and current medications for PNH. Concomitant medications and procedures will be recorded from the first infusion of study drug through 56 days after the patient's last dose of study drug. Any changes in concomitant medications also will be recorded in the patient's source document/medical chart and eCRF. Any concomitant medication deemed necessary for the patient's standard of care during the study, or for the treatment of any AE, along with the allowed medications described below may be given

at the discretion of the Investigator. However, it is the responsibility of the Investigator to ensure that details regarding all medications are recorded in full in the patient's source document/medical chart and eCRF.

Concomitant use of anticoagulants is prohibited if not on a stable dose regimen for at least 2 weeks prior to Day 1.

Concomitant use of complement inhibitors other than the study treatment is prohibited.

9.8. Vaccination

Due to its mechanism of action, the use of ALXN1210 increases the patient's susceptibility to meningococcal infection (*N meningitidis*). To reduce the risk of meningococcal infection, all patients must be vaccinated against meningococcal infections within 3 years prior to, or at the time of, initiating study drug. Patients who initiate study drug treatment less than 2 weeks after receiving a meningococcal vaccine must receive treatment with appropriate prophylactic antibiotics until 2 weeks after vaccination. Vaccines against serotypes A, C, Y, W135, and B, where available, are recommended to prevent common pathogenic meningococcal serotypes. Patients must be vaccinated or revaccinated according to current national vaccination guidelines or local practice for vaccination use with eculizumab. Vaccination may not be sufficient to prevent meningococcal infection. Consideration should be given per official guidance and local practice on the appropriate use of antibacterial agents and vaccination. All patients should be monitored for early signs of meningococcal infection, evaluated immediately if infection is suspected, and treated with appropriate antibiotics, if necessary.

To increase risk awareness and promote quick disclosure of any potential signs or symptoms of infection experienced by the patients during the course of the study, patients will be provided a safety card to carry with them at all times. Additional discussion and explanation of the potential risks, signs, and symptoms will occur at each visit as part of the review of the patient safety card as described in the Schedule of Assessments (Section 7.3).

Patients must also be vaccinated against Hib and *S pneumoniae* according to national and local vaccination schedule guidelines.

Vaccinations for *N meningitidis*, Hib, and *S pneumoniae* will be recorded on the patient's eCRF.

9.9. Treatment Compliance

Patients will be administered study drug in a controlled setting under the supervision of the Investigator or designee, thereby ensuring compliance with study drug administration. The Investigator or designee will ensure that all patients are adequately informed on the specific dosing regimen required for compliance with the study protocol, ensure that the patient receives the appropriate dose at the designated time points during the study and that adequate safety monitoring occurs during the infusion (Section 9.5).

9.10. Home Visits

To ensure patient safety and treatment continuity during the COVID-19 pandemic, the following will apply where patients are not able to reach the study sites, and until patients are able to resume study visits at the site.

Patients may have an opportunity to receive ALXN1210 administration remotely at a medical facility that is located near the patient's home or at the patient's home with the permission of the Investigator in accordance with all national, state, and local laws or regulations of the pertinent regulatory authorities. Home infusions may be considered only for patients who have tolerated previous drug infusions well, without clinically significant infusion reactions, at the study site.

Remote visit options may be at the Investigator's discretion and oversight, in accordance with the local regulations, and conducted by a qualified medical professional. Information about AEs, concomitant medications, and signs and symptoms of breakthrough hemolysis must be sent to the Investigator's site for evaluation on the day of the remote visit. In case of any signs or symptoms indicating an SAE or breakthrough hemolysis, the patient will need to be evaluated at the study site.

Monitoring, treatment, and management of infusion reactions for patients receiving drug infusions at home are described in detail in the home health care manual and Appendix B.

9.11. Contraception Guidance

Female patients of childbearing potential (ie, who have achieved menarche) must use a highly effective or acceptable method of contraception (as defined below), starting at Screening and continuing for at least 8 months after the last dose of study drug.

Highly effective contraceptive methods include:

- 1. Hormonal contraception associated with inhibition of ovulation
- 2. Intrauterine device
- 3. Intrauterine hormone-releasing system
- 4. Bilateral tubal occlusion
- 5. Vasectomized partner, provided that the partner is the patient's sole sexual partner
- 6. Sexual abstinence, defined as refraining from heterosexual intercourse during the entire period of risk associated with the study drug treatment; reliability of sexual abstinence needs to be evaluated in relation to the duration of the clinical study and the preferred and usual lifestyle of the patient

Acceptable contraceptive methods include:

1. A combination of male condom with either cap, diaphragm, or sponge with spermicide (double barrier methods)

The above-listed method(s) of contraception chosen for an individual patient can be determined by the Investigator with consideration for the patient's medical history and concomitant medications.

Male patients with a female spouse/partner of childbearing potential or a pregnant or breastfeeding spouse or partner must agree to use double barrier contraception (male condom plus appropriate barrier method for the female partner) while on treatment and for at least 8 months after the last dose of study drug. Double barrier contraception is required even with documented medical assessment of surgical success of a vasectomy.

Male patients must not donate sperm while on treatment and for at least 8 months after the last dose of study drug.

10. EFFICACY ASSESSMENTS

10.1. Transfusions

Administration of a pRBC transfusion, including the hemoglobin result and symptoms that triggered the transfusion, and the number of units transfused, will be documented in the eCRF.

10.2. Lactate Dehydrogenase and Other Disease-Related Laboratory Parameters

Blood and urine samples will be collected at the times indicated in the Schedule of Assessments (Section 7.3) and as indicated in Section 11.4.

The following disease-related laboratory parameters will be measured during the study (refer to Section 12 for PK/PD assessments):

- LDH
- free hemoglobin
- occult blood, urine
- total C5
- haptoglobin
- reticulocyte count
- PNH RBC clone size evaluated by high-sensitivity flow cytometry (Borowitz, 2010)
- estimated glomerular filtration rate (calculated using the Schwartz formula)

10.3. Paroxysmal Nocturnal Hemoglobinuria Symptomatology

The Investigator or designee will record for each patient the presence or absence of the following signs and symptoms of PNH: fatigue, chest pain, abdominal pain, dyspnea, dysphagia, erectile dysfunction, and red/dark urine or hemoglobinuria.

10.4. Quality of Life

The Pediatric FACIT-Fatigue scale is a 13-item questionnaire that assesses fatigue and its impact upon daily activities and function over the preceding 7 days. Each item is scored on a 5-point scale, and total scores range from 0 to 52, with higher score indicating better QoL. The questionnaire will be self-reported by patients who were ≥ 8 years of age at the time of enrollment and reported by caregivers for patients who were ≥ 5 to < 8 years of age at the time of enrollment. Patients < 5 years of age will not be assessed. The Pediatric FACIT-Fatigue scale is shown in Appendix C.

10.5. Major Adverse Vascular Events

Major adverse vascular events will be assessed as part of the planned evaluation for AEs as described in Section 11.7.

The description of the MAVE including the method of diagnosis (eg, magnetic resonance imaging, ultrasound, angiogram), date of diagnosis, and date resolved (or ongoing) will be collected on the eCRF as part of the patient's medical history (prior to baseline).

A MAVE is defined as follows:

- Thrombophlebitis/deep vein thrombosis
- Pulmonary embolus
- Myocardial infarction
- Transient ischemic attack
- Unstable angina
- Renal vein thrombosis
- Acute peripheral vascular occlusion
- Mesenteric/visceral vein thrombosis or infarction
- Mesenteric/visceral arterial thrombosis or infarction
- Hepatic/portal vein thrombosis (Budd-Chiari syndrome)
- Cerebral arterial occlusion/cerebrovascular accident
- Cerebral venous occlusion
- Renal arterial thrombosis
- Gangrene (nontraumatic; nondiabetic)
- Amputation (nontraumatic; nondiabetic)
- Dermal thrombosis
- Other, specify

11. SAFETY ASSESSMENTS

The Investigator or his/her designee will meet with patients to discuss the potential safety risks of ALXN1210 and to give the Investigator the opportunity to address any of the patient's safety concerns regarding the study.

Investigators are instructed to follow any AEs through to their conclusion (resolution or stabilization), as described in Section 11.7.6.

The timing of the clinical and laboratory assessments to be performed is specified in the Schedule of Assessments (Section 7.3). Any clinically significant abnormal results should be followed until resolution or stabilization.

11.1. Demographic/Medical History

11.1.1. Demographics and Baseline Characteristics

A review of demographic parameters, including age, gender, race, and ethnicity will be performed. A complete medical history will be taken and documented. Weight and height will be recorded. Head circumference will be recorded for patients who are ≤ 3 years of age.

11.1.2. Disease Characteristics

The patient's PNH medical history, including PNH symptoms, date of diagnosis, PNH clone size, pRBC transfusions, and history of any MAVEs, will be documented at the Screening Visit.

11.1.3. Medical History

The patient's medical history, including prior and concomitant conditions/disorders and transfusion history, will be recorded at the Screening Visit. Medication (prescription or over-the-counter, including vitamins and/or herbal supplements) use within 28 days prior to the start of Screening will also be recorded. Details of prior treatment with eculizumab, including dose level and frequency, will be collected.

Meningococcal vaccination within 3 years prior to the first dose of study drug, and vaccination history for Hib and *S pneumoniae* from birth, will also be recorded, as described in Section 9.7.

11.2. Physical Examinations

A physical examination will include the following assessments: general appearance; skin; head, ear, eye, nose, and throat; neck; lymph nodes; chest; heart; abdominal cavity; limb; central nervous system; and musculoskeletal system. An abbreviated physical examination consists of a body system relevant examination based upon Investigator (or qualified designee) judgment and patient symptoms. Physical growth (height, weight, and head circumference [the latter only in patients ≤ 3 years of age]) will be assessed.

11.3. Vital Signs

Vital sign measurements will be taken after the patient has been resting for at least 5 minutes, and will include systolic and diastolic blood pressure (BP; millimeters of mercury [mmHg]),

heart rate (beats/minute), respiratory rate (breaths/minute), and temperature (degrees Celsius [°C] or degrees Fahrenheit [°F]).

11.4. Laboratory Assessments

Samples for serum pregnancy, hematology, chemistry, coagulation, and urinalysis will be performed at the times specified in the Schedule of Assessments (Section 7.3). Specific laboratory assessments are provided in Appendix D. Samples for laboratory assessments will be collected before each study drug administration. An alternative blood sampling schedule for infants, for whom less blood volume should be collected, must be used as detailed in the laboratory manual. If a suspected event of breakthrough hemolysis occurs, an unscheduled visit must take place at which a sample is collected for analysis of LDH and PK/PD by the central laboratory.

Laboratory assessments will be tested at a central laboratory facility. Please refer to the Laboratory Manual for time windows for collection and detailed instructions for collecting, processing, storing, and shipping blood samples for safety assessments. Laboratory reports will be made available to the Investigators in a timely manner for clinical management of patients.

It is anticipated that some laboratory values may be outside the normal value range due to the underlying disease. The Investigators should use their medical judgment when assessing the clinical significance of these values. Clinical significance is defined as any variation in laboratory measurements that has medical relevance and which results in a change in medical care. If clinically significant laboratory changes from baseline value are noted, the changes will be documented as AEs on the AE eCRF. The Investigator will also assess the relationship to study treatment for all clinically significant out-of-range values (Section 14.9.3). The Investigator will continue to monitor the patient through additional laboratory assessments until (1) values have returned to the normal range or baseline level, or (2) in the judgment of the Investigator, values that are outside the normal range are not related to the administration of study drug or other protocol-specific procedures.

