5. INTRODUCTION

Paroxysmal nocturnal hemoglobinuria (PNH) is a progressive, debilitating, and life-threatening disease characterized by complement-mediated hemolysis, thrombosis, and bone marrow failure. PNH has an estimated worldwide incidence of 1.3 per million population (Hill, 2006). The onset of PNH is typically in adulthood, with pediatric cases accounting for < 5% of reported cases (Ware, 1991). Given the extremely small target population, studies of children with PNH have been limited to case reports, case series, and a small clinical trial (Reiss, 2014).

In adults, the clinical manifestations of PNH include hemoglobinuria, chronic renal insufficiency, erectile dysfunction, thrombosis, abdominal pain, dyspnea, and dysphagia (Parker, 2005). In contrast, children with PNH usually present with nonspecific symptoms related to the underlying bone marrow disorder, such as pallor, fatigue, or jaundice, with hemoglobinuria appearing less commonly (Ware, 1991). Clinical evaluation in pediatric patients also reveals bone marrow failure syndromes, such as aplastic anemia and refractory cytopenia (van den Heuvel-Eibrink, 2007). Once the bone marrow disorder is resolved in the child or the PNH clone expands (the cause of which is still unknown), the disease eventually evolves into one more typically seen in adults at presentation. Thus, pediatric patients can be expected to suffer substantial morbidity related to hemolysis, as seen in adult PNH patients (Parker, 2005).

The ALXN1210 clinical program in patients with PNH includes a Phase 3 study in adults with PNH who are naïve to eculizumab therapy, a Phase 3 study in adults with PNH who are stable on eculizumab therapy, a Phase 1b dose-ranging study, and a Phase 2 dose regimen optimization study. Each of these studies also includes a 2-year extension phase. In addition, a Phase 1 study to assess the pharmacokinetic (PK) profile of ALXN1210 in healthy Japanese subjects has been completed.

In this Phase 3, open-label study, the PK, pharmacodynamics (PD), efficacy, and safety of ALXN1210 will be assessed in pediatric patients with PNH. The study design rationale is further discussed in Section 7.2.

More information about the PK, mechanism of action, known and expected benefits, risks, and reasonably anticipated adverse events (AEs) of ALXN1210 may be found in the current edition of the Investigator's Brochure (IB).

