8.1. Inclusion Criteria

Patients are eligible for enrollment in the study only if they meet all of the following criteria and none of the exclusion criteria:

- 1. Male and female patients < 18 years of age and weighing ≥ 5 kg at the time of consent.
- 2. Documented diagnosis of PNH, confirmed by high-sensitivity flow cytometry evaluation (Borowitz, 2010) of red blood cells (RBCs) and white blood cells (WBCs), with granulocyte or monocyte clone size of \geq 5%.
- 3. For patients not currently treated with eculizumab, presence of 1 or more of the following PNH-related signs or symptoms within 3 months of Screening: fatigue, hemoglobinuria, abdominal pain, shortness of breath (dyspnea), anemia, history of a major adverse vascular event (including thrombosis), dysphagia, or erectile dysfunction; or history of packed red blood cell (pRBC) transfusion due to PNH.
- 4. Lactate dehydrogenase (LDH) values at Screening as follows:
 - a. For patients not currently treated with eculizumab, LDH level $\geq 1.5 \times \text{ULN}$.
 - b. For patients who are currently taking eculizumab, LDH $\leq 1.5 \times$ ULN (sample must be obtained on a scheduled eculizumab-dosing day prior to dose administration [ie, at trough eculizumab level] and analyzed by the central laboratory).
- 5. To reduce the risk of meningococcal infection (*N meningitidis*), all patients must be vaccinated against meningococcal infections within 3 years prior to, or at the time of, initiating study drug. Patients who initiate study drug treatment less than 2 weeks after receiving a meningococcal vaccine must receive treatment with appropriate prophylactic antibiotics until 2 weeks after vaccination. Patients who cannot be vaccinated must receive antibiotic prophylaxis for the entire treatment period and for 8 months following last dose.
- 6. Patients must have been vaccinated against *Haemophilus influenzae* type b (Hib) and *Streptococcus pneumoniae* according to national and local vaccination schedule guidelines, as appropriate.
- 7. Female patients of childbearing potential (ie, have achieved menarche) and male patients with female partners of childbearing potential must follow protocol-specified guidance for avoiding pregnancy while on treatment and for 8 months after last dose of study drug.

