8.2. Exclusion Criteria

Patients will be excluded from study enrollment if they meet any of the following criteria:

- 1. Platelet count $< 30,000/\text{mm}^3 (30 \times 10^9/\text{L})$ at Screening.
- 2. Absolute neutrophil count $< 500/\mu L$ (0.5 × 10⁹/L) at Screening.
- 3. History of bone marrow transplantation.
- 4. History of *N meningitidis* infection.
- 5. History of unexplained, recurrent infection.
- 6. Active systemic bacterial, viral, or fungal infection within 14 days prior to study drug administration on Day 1.
- 7. History of malignancy within 5 years of Screening with the exception of adequately treated nonmelanoma skin cancer or carcinoma in situ of the cervix.
- 8. History of or ongoing major cardiac, pulmonary, renal, endocrine, or hepatic disease (eg, active hepatitis) that, in the opinion of the Investigator or Sponsor, precludes the patient's participation in an investigational clinical trial.
- 9. Unstable medical conditions (eg, myocardial ischemia, active gastrointestinal bleed, severe congestive heart failure, anticipated need for major surgery within 6 months of Screening, coexisting chronic anemia unrelated to PNH) that would make them unlikely to tolerate the requirements of the protocol.
- 10. Concomitant use of anticoagulants is prohibited if not on a stable regimen for at least 2 weeks prior to Day 1.
- 11. History of hypersensitivity to any ingredient contained in the study drug, including hypersensitivity to murine proteins.
- 12. Females who plan to become pregnant or are currently pregnant or breastfeeding.
- 13. Females of childbearing potential who have a positive pregnancy test result at Screening or on Day 1.
- 14. Participation in another interventional treatment study or use of any experimental therapy within 30 days before initiation of study drug on Day 1 in this study or within 5 half-lives of that investigational product, whichever is greater.
- 15. Known or suspected history of drug or alcohol abuse or dependence within 1 year prior to the start of Screening.
- 16. Known medical or psychological condition(s) or risk factor that, in the opinion of the Investigator or Sponsor, might interfere with the patient's full participation in the study,

pose any additional risk for the patient, or confound the assessment of the patient or outcome of the study.

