11.7.2. Severity Assessment

The severity of AEs will be graded using Common Terminology Criteria for Adverse Events (CTCAE) version 4.03 or higher. A grading (severity) scale is provided for each AE term. Each CTCAE term is a Lowest Level Term (LLT) per the Medical Dictionary for Regulatory Activities (MedDRA®). Each LLT will be coded to a MedDRA preferred term (PT).

Grade refers to the severity of the AE. The CTCAE assigns a grade of 1 through 5, with unique clinical descriptions of severity for each AE (Table 7).

Table 7:	Adverse	Event Severity	Grading Scale
----------	---------	----------------	----------------------

Grade	Description
Grade 1	Mild; asymptomatic or mild symptoms; clinical or diagnostic observations only; intervention not indicated
Grade 2	Moderate; minimal, local or noninvasive intervention indicated; limiting age-appropriate instrumental ADL ^a
Grade 3	Severe or medically significant, but not immediately life-threatening; hospitalization or prolongation of hospitalization indicated; disabling; limiting self-care ADL ^b
Grade 4	Life-threatening consequences; urgent intervention indicated.
Grade 5	Death related to AE.

Abbreviations: ADL = activities of daily living; AE = adverse event

Any change in the severity of an AE should be documented based on specific guidelines in the eCRF Completion Guidelines.

Severity and seriousness must be differentiated: severity describes the intensity of an AE, while the term seriousness refers to an AE that has met specific criteria for an SAE as described in Section 11.7.4.

^a Instrumental ADL refers to preparing meals, shopping for groceries or clothes, using the telephone, managing money, etc.

^b Self-care ADL refers to bathing, dressing and undressing, feeding self, using the toilet, taking medications, and not bedridden.

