7.3.3. Other Safety

7.3.3.1. Analyses for Laboratory Tests

Descriptive statistics by visit will be presented for each central laboratory parameter and for changes from baseline (continuous variables), by naïve, previously eculizumab-treated patients, and total. baseline is defined as the last non-missing assessment value prior to the first ALXN1210 infusion. Shift tables over time will be presented for all central laboratory values, where applicable, using normal, low, or high based on normal range values. For purposes of analyses, laboratory results based upon standardized units will be used. Individual patient plots as well as box plots will be presented for the following central lab parameters: hemoglobin, haptoglobin, hematocrit, reticulocytes, LDH, bilirubin, direct bilirubin, creatinine, AST, ALT, and GGT.

All central and local laboratory data will be presented in by-patient listings.

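### Low/normal/high laboratory shift tables cannot show a further fall in platelets or neutrophils that are already low at baseline, and no other planned summary ties the worst value to baseline severity

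*Protocol*

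**What the plan says.** Protocol 14.9.3 and SAP 7.3.3.1 set the same rule: "Shift tables over time will be presented for all central laboratory values, where applicable, using normal, low, or high based on normal range values". Neither plans a shift by toxicity grade or by distance below a limit. CTCAE grading is stated for adverse events only (Protocol 11.7.2): "The severity of AEs will be graded using Common Terminology Criteria for Adverse Events (CTCAE) version 4.03 or higher".

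Protocol 11.4 says of the laboratory data: "It is anticipated that some laboratory values may be outside the normal value range due to the underlying disease". The Protocol's Introduction adds: "Clinical evaluation in pediatric patients also reveals bone marrow failure syndromes, such as aplastic anemia and refractory cytopenia". Protocol 8.2 excludes only platelets below 30 x 10^9/L and neutrophils below 0.5 x 10^9/L.

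Other planned displays of laboratory data are:
- by-visit statistics, with changes from baseline, for every central parameter (SAP 7.3.3.1);
- individual and box plots for eleven named parameters (SAP 7.3.3.1);
- by-patient listings of all laboratory data (SAP 7.3.3.1), and listings of patients with abnormal results (Protocol 14.9.3);
- adverse-event reports for clinically significant changes (Protocol 11.4).

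**The concern.** A shift table is meant to show which patients moved, and in which direction, from where they started. With three categories it shows movement across a limit of normal and nothing beyond it. In a disease with marrow failure, where cytopenic children are eligible, some patients will probably start in the low cell. A further fall in their counts then appears as no shift.

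Laboratory assessments are a stated safety endpoint (Protocol 6.2.3). Neutrophils deserve particular care because increased susceptibility to meningococcal infection is the main risk the Protocol names for the drug (5.1.2.1).

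**Working it through.** **1. The classification rule.** Let L be the lower limit of normal, b the baseline and p a later value. If b < L and p < b, then p < L, so the pair is always low-to-low, whatever the size of the fall. The documents give no value for L. Falls in platelets from 90 to 29 or from 40 to 10 x 10^9/L are low-to-low with L at either 100 or 150. With L = 150 a fall from 149 to 30 (149/30 = 5.0-fold) does not register. With L = 1.5 for neutrophils, nor does a fall from 1.49 to 0.5 (1.49/0.5 = 3.0-fold).

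**2. Which parameters have other cover.**

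| Parameter | Individual and box plots (SAP 7.3.3.1) | Own analysis |
|---|---|---|
| LDH | yes | yes: percent change, counts at 1.0 and 1.5 x ULN, breakthrough at 2 x ULN |
| Hemoglobin | yes | yes: 2 g/dL decrease from baseline |
| ALT, AST, bilirubin, creatinine | yes | no |
| Platelets | no | no |
| Neutrophils | no | no |

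Platelets and the white-cell differential are both collected (Protocol Appendix D).

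**3. What the by-visit summaries keep.** SAP 9.3 uses one record per analysis window, the one closest to the window's midpoint. For hematology the Day 71 window runs from Day 57 to Day 84, with midpoint (57 + 84)/2 = 70.5. An unscheduled count on, say, Day 62 lies 8.5 days from the midpoint and the scheduled Day 71 count lies 0.5 days from it. Only the Day 71 count enters the summary, even if Day 62 was the nadir.

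**4. Size, under stated assumptions.** The plan gives no figure to reproduce. Assume a lognormal baseline with median m and log-SD 0.6, cut at the entry floor f (30 or 0.5), with L = 150 or 1.5, and halve every count. With F(x) = Φ((ln x − ln m)/0.6):
- low-to-low = (F(L) − F(f)) / (1 − F(f))
- visible shift = (F(2L) − F(L)) / (1 − F(f))
- low at neither time = (1 − F(2L)) / (1 − F(f))

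For platelets with m = 100, F(30) = 0.0224, F(150) = 0.7504 and F(300) = 0.9665. Low-to-low = (0.7504 − 0.0224)/0.9776 = 0.745. Visible shift = (0.9665 − 0.7504)/0.9776 = 0.221. Low at neither time = 0.0335/0.9776 = 0.034.

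| Count (x 10^9/L) | Median m before the cut | Low-to-low | Visible shift | Low at neither time |
|---|---|---|---|---|
| Platelets | 60 | 93% | 7% | <1% |
| Platelets | 100 | 74% | 22% | 3% |
| Platelets | 150 | 50% | 38% | 12% |
| Neutrophils | 0.9 | 76% | 21% | 3% |
| Neutrophils | 1.5 | 48% | 39% | 13% |
| Neutrophils | 2.5 | 19% | 42% | 38% |

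Only the low-to-low column measures this gap. Children who are low at neither time also show no shift, but for a different reason. Rows may not sum to 100% because of rounding.

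With a platelet limit of 100 instead of 150, the same formula gives (0.8027 − 0.1240)/0.8760 = 77%, (0.5000 − 0.0224)/0.9776 = 49% and (0.2496 − 0.0037)/0.9963 = 25% for the three medians.

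**The case against.** The strongest reply is that the shift table is not the main laboratory display. SAP 7.3.3.1 plans change-from-baseline statistics by visit for every central parameter, and SAP 7 fixes these to include the minimum. The minimum change is the largest within-child fall at that visit, and it does use the child's own baseline. About 13 patients are planned, and this SAP covers the report after 12 are enrolled, so listings can be read child by child. A grade-by-grade grid split by prior treatment would be mostly empty. All of this stands, and it limits the consequence. It does not close the gap: the minimum change and the minimum value need not belong to the same child, neither shows how low that child started, and both are taken after the one-record rule.

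The adverse-event route also counts for something. Protocol 11.7 lets an abnormal laboratory finding be an adverse event, and SAP 5.3.1 counts exacerbations of pre-existing conditions as adverse events. But under Protocol 11.4, "Clinical significance is defined as any variation in laboratory measurements that has medical relevance and which results in a change in medical care". A large fall that is only watched may therefore not be recorded as an event. Cover by this route depends on investigator judgment.

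A reader might infer that LDH is affected equally, since patients not on eculizumab must enter at or above 1.5 x ULN and so start high. The shift table is indeed uninformative there, but LDH has the separate analyses shown in the working, and nobody needs the shift table to follow it.

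**Conclusion.** The gap is real and narrow. For platelets and neutrophils, no planned summary ties a child's worst value to that child's baseline severity. Step 1 of the working needs no assumption beyond a low baseline. The percentages rest on assumed medians, spread, lower limits and a universal halving, none of which the documents give, so they illustrate the range and are not forecasts.

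Two stronger readings are not supported. A reader might conclude that worsening would go unseen in the trial; the other displays would show much of it. A reader might also take the sentence in Protocol 11.4 as a statement about baseline values, or as a sign that the drug lowers counts. It says neither: the expectation of low baselines comes from the entry criteria and the Introduction, and nothing in the documents suggests a drug effect on counts.

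The study is descriptive and no test is affected. This is a worthwhile, inexpensive improvement to the safety reporting.

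**What to change.** In SAP 7.3.3.1:
- For platelets and neutrophils, and optionally other parameters with a CTCAE laboratory grade, add a table of baseline grade against worst post-baseline grade. Use all central laboratory records, including unscheduled ones, and give the number of patients worsening by at least one grade.
- Add platelets and neutrophils to the individual and box plots.
- Keep the low/normal/high tables alongside.
- Keep the existing exclusion of tabletop-hemolysis values for the affected chemistry parameters. It does not touch platelets or neutrophils.

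The cost is SAP wording and a few sparse tables and plots from data already collected, with no change in conduct. A fall within one grade would still show as no shift, which is why the plots are part of the change. Neither document reproduces the CTCAE laboratory cut-offs, and some may not be age-specific, so their suitability across the age range should be checked when the table is specified.
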